1. INTRODUCTION AND OBJECTIVES

The purpose of the study is to evaluate the safety and efficacy of GLASSIA as an add-on biopharmacotherapy to standard-of-care steroid treatment as the first-line treatment in subjects with acute graft-versus-host disease (GvHD) with lower gastrointestinal (GI) involvement. This is a 2-part study. Part 1 will evaluate the safety, efficacy and pharmacokinetic (PK) of GLASSIA in approximately 20 subjects. Start of any Part 2 activities was pending results from statistical analysis of Part 1 data.

GLASSIA was approved in the United States for chronic augmentation and maintenance therapy in individuals with emphysema due to congenital deficiency of human alpha-1 proteinase inhibitor (A₁PI). The preclinical literature for A₁PI, in combination with the interim efficacy results from a Phase 1/2 study, suggests that GLASSIA has the potential to provide significant clinical benefit as a first-line treatment in acute GvHD. There is currently no FDA-approved treatment for acute GvHD. The study population is selected because severe acute GI GvHD is associated with high mortality and patients with acute GvHD with lower GI involvement have a lower response rate to steroid treatment.

On 2 June 2017, Shire (sponsor) prematurely terminated the entire study (both Part 1 and Part 2) following an internal portfolio prioritization exercise which took into consideration difficulties in enrolling subjects and a reduced probability of success of the study. As of the decision date, only 1 subject had been enrolled in the study and no additional subject will be enrolled. That subject was treated with study drug under the original protocol because Protocol Amendment 1, while approved on 19 April 2017, prior to the study termination date, could not be implemented.

This SAP is for Part 1 of the 2-part study and is based on the original protocol and thus documents all derivations of outcome variables, statistical analyses and summaries preplanned in the original protocol. Derivations of outcome variables, statistical analyses and summaries in this SAP are no longer applicable, as indicated by “Not Applicable” in the appropriate sections, but the analysis content is retained only for alignment with the original protocol. Only data listings will be produced for the single-enrolled subject, and the listings will include raw (actual) values. In addition, since no adjudication of the response assessment data will be done, only the data based on the investigators’ assessments will be presented in the listings.

There will be no SAP for Part 2 since the entire study (Part 1 and Part 2) was terminated before start of Part 2. No subjects were enrolled in Part 2 at time of termination.

1.1 Study Objectives

1.1.1 Primary Objective

To confirm the safety and efficacy of GLASSIA administered at a dose of 90 mg/kg (Day 1) followed by 30 mg/kg every other day (Days 3 to 13), then followed by 120 mg/kg weekly (Days 15 to 50), when added to conventional steroid therapy, in subjects with acute GvHD with Stage 1 to 4 lower GI involvement, as assessed by treatment response at Day 28, and to determine whether continuation to Part 2 is warranted.

1.1.2 Secondary Objective(s)

1.1.2.1 Efficacy

To evaluate the treatment effects of GLASSIA, when added to conventional steroid therapy, on other clinical outcomes, such as rate, duration and magnitude of response; all-cause, transplant-related, infection-related and GvHD-related mortality; overall survival; GvHD-free survival; treatment failure-free survival and incidence of chronic GvHD.

1.1.2.2 Safety

1. To evaluate the safety and tolerability of GLASSIA in addition to conventional steroid therapy (Part 1)
2. To assess the incidence of recurrence of primary malignancies
3. To assess the incidence and type of infection

1.1.2.3 Pharmacokinetics

To characterize the PK profile of GLASSIA, when added to conventional steroid treatment, using noncompartmental analysis methodology.

1.1.2.4 Exploratory

1. To assess A₁PI plasma and stool concentrations and clearance in stool
2. To characterize the PK profile of GLASSIA, when added to conventional steroid treatment, using a population PK approach
3. To assess biomarkers in plasma (ie, inflammatory cytokines IL-2, IL-6, IL-8, IL-10 and IL-32; heparan sulfate; regenerating islet-derived protein 3 α [Reg3 α]; suppression of tumorigenicity 2 (ST2); tumor necrosis factor receptor 1 [TNFR1]; IL-1 receptor antagonist [IL-1RA] and T cell subpopulations, including CD4⁺ CD25⁺ CD127⁺ FoxP3⁺ Tregs) and stool (ie, calprotectin concentrations)

4. To assess quality-of-life (QoL), GvHD symptoms and healthcare resource utilization for GLASSIA treatment as a first-line add-on therapy

2. STUDY DESIGN

This is a 2-part Phase 2/3, prospective, controlled, randomized, multicenter study in subjects with acute GvHD with Stage 1 to 4 lower GI involvement. Part 1 of this study is a nonrandomized, open-label, multicenter, clinical study evaluating GLASSIA in combination with conventional steroid treatment. The target population for Part 1 will include approximately 20 subjects (Cohort 1). The overall study design of Part 1 is illustrated in Figure 1 in Section 14.1. Part 2 of the study is not discussed in this SAP.

Screening for eligibility will occur from Days -2 to -1. After screening, all eligible subjects will be given GLASSIA with a loading dose of 90 mg/kg (Day 1) followed by GLASSIA 30 mg/kg every other day (Days 3 to 13), then followed by 120 mg/kg weekly (Days 15 to 50) in combination with 2 mg/kg/day of methylprednisolone or equivalent steroid. Tapering of steroids may commence after a subject responds to therapy.

All subjects will be treated through Day 50, or until treatment failure, withdrawal from treatment or withdrawal from the study, whichever comes first. Thereafter, subjects will be treated with standard-of-care for the remainder of their participation in the study based on the investigator's discretion. Prior to Day 28, subjects must be withdrawn from study treatment if a second-line treatment for acute GvHD is introduced. Subjects who experience recurrent malignancy will also be withdrawn from study treatment. Subjects who are withdrawn from study treatment will continue to be followed through at least Day 28, unless the subject withdraws consent.

Steroid treatment after Day 50 will be at the investigator's discretion. Subjects will visit the site for follow-up visits on Days 56, 100, 180 and 365. In the event that it is not feasible for the subject to visit the site at Day 365, the visit may be conducted with a phone call.

Subjects requiring second-line treatment after Day 56 may be eligible to receive 1-time retreatment with GLASSIA with the same loading and maintenance dosing regimen (50 days of treatment). Regardless of whether the subject receives retreatment, all subjects will be followed up at Days 100, 180 and 365.

Subjects classified as treatment failures will be included in the analysis but not be counted as either complete response (CR) or partial response (PR) for the primary

(overall response) or key secondary (GI response) endpoints. Subjects classified as treatment failures will not be replaced. Assessments of vital signs, clinical laboratory data (hematology and chemistry), local tolerability and adverse events (AEs) will be performed throughout the study.

2.1 Study Population

The population for this study will consist of male and female subjects ≥ 18 years of age who are recipients of an allogeneic hematopoietic stem cell transplantation (HSCT) and who have been newly diagnosed with acute GvHD with lower GI involvement (modified International Bone Marrow Transplant Registry [IBMTR] Severity Stage 1 to 4). Subjects with Stage 1 to 4 lower GI involvement have diarrhea >500 mL/day. Subjects must have evidence of myeloid engraftment. There are no restrictions on the prior conditioning treatments.

2.2 Sample Size and Power Calculations

The sample size for Part 1 was determined from an operational perspective and was not based on statistical power considerations. With 20 subjects and an assumed true response rate of 65%, the probability of observing an overall response rate of at least 55% is 87.8%. If the true response rate is 40%, the probability of observing an overall response rate of 55% or higher is less than 13%.

2.3 Randomization and Blinding

Part 1 is a nonrandomized, open-label, active treatment clinical study.

2.4 Study Stopping Rules

Stopping rules will not be established for Part 1 of this study. The study may be stopped at the sponsor's discretion for any reason, including lack of efficacy, toxicities or adverse safety findings.

2.5 Study Assessments

A schedule of assessments for Part 1 is provided in Section [14.2](#). Details on clinical laboratory assessments can be found in Section [14.3](#).

2.6 Withdrawal and Discontinuation

Any subject may voluntarily withdraw (ie, reduce the degree of participation in the study) consent for continued participation and data collection.

Discontinuation (ie, complete withdrawal from study participation) may be due to dropout (ie, active discontinuation by subject) or loss to follow-up (ie, discontinuation by subject without notice or action). Additionally, the investigator and sponsor have the discretion to discontinue any subject from the study if, in their judgment, continued participation would pose an unacceptable risk for the subject.

Subjects also will be withdrawn from treatment or discontinued from further study participation for the following reasons:

- The subject has a lower GI biopsy that in the opinion of a pathologist is inconsistent with acute GvHD
- The subject becomes pregnant
- The subject begins lactating
- The subject starts a second-line treatment for acute GvHD prior to Day 28
- The subject experiences recurrent malignancy

2.7 Data Monitoring Committee

A Data Monitoring Committee (DMC) will independently evaluate safety and efficacy data. For this study, the DMC will be composed of recognized experts in the fields of oncology, hematology and immunology clinical care and research who are not actively recruiting subjects. The DMC may make a recommendation to continue the study as is, temporarily suspend the study, continue the study after proper amendment to the protocol or terminate the study based on predefined criteria such as unacceptable toxicities or lack of treatment benefits.

The DMC will meet periodically to evaluate safety during Part 1 and use the results from Part 1 to determine whether continuation to Part 2 is warranted. The DMC may meet in ad hoc meetings at its discretion as needed in response to events occurring in the study. The DMC's responsibilities, definitions and operating procedures will be defined in a charter; the committee will maintain records of all its meetings.

3. STUDY OUTCOME MEASURES

3.1.1 Primary Outcome Measure

The primary outcome measure for Part 1 is the proportion of subjects achieving overall response (GvHD CR + PR) at Day 28.

3.1.2 Secondary Outcome Measures

3.1.2.1 Efficacy

Key Secondary Efficacy Outcome Measures

1. Proportion of subjects achieving GI response (GI CR + PR) at Day 28

Other Secondary Efficacy Outcome Measures

1. Proportion of subjects achieving overall response at Day 56
2. Change from baseline in acute GvHD grading at Days 28, 56 and 180
3. Incidence of chronic GvHD at Days 100, 180 and 365
4. Duration of any overall response
5. Duration of any GI response
6. Overall survival through Days 100, 180 and 365
7. Transplant-related mortality at Days 28, 56, 100 and 180
8. Failure-free survival at Days 100 and 180
9. GvHD-free survival at Days 28, 56, 100 and 180
10. Infection-related mortality at Days 28, 56, 100 and 180
11. GvHD-related mortality at Days 28, 56, 100 and 180
12. All-cause mortality at Days 28, 56, 100 and 180

3.1.2.2 Safety

1. The incidence and severity of all AEs, related AEs, all SAEs, related SAEs and temporally-associated AEs
2. Change from baseline in clinical laboratory safety parameters and vital signs
3. Incidence of recurrence of primary malignancies through Days 180 and 365
4. Incidence and type of infection (eg, bacterial, fungal, viral, etc) at Days 28, 56, 180 and 365

3.1.3 Exploratory Outcomes Measure

3.1.3.1 Efficacy

1. Proportion of subjects achieving GvHD very good partial response (VGPR) at Day 28
2. Cumulative steroid dose at Days 28, 56, 100 and 180
3. Steroid dose at Days 28, 56 and 100
4. Proportion of subjects achieving GI CR and GI PR at Days 28, 56 and 180 at each baseline GvHD severity grade (B, C and D)

3.1.3.2 Pharmacokinetics

The following noncompartmental analysis PK parameters by day and/or dosing frequency, as applicable, will be assessed:

1. Area under the plasma concentration curve (AUC) from time zero to the last quantifiable activity
2. AUC from time zero to time “t”
3. Systemic clearance at steady state
4. Maximum plasma concentration at steady state
5. AUC from time zero to infinity
6. Apparent volume of distribution at steady state
7. The terminal half-life
8. Mean residence time
9. Trough plasma A1PI levels at steady state

3.1.3.3 Pharmacodynamics

1. Change from baseline in plasma and stool concentrations of A1PI
2. A1PI clearance in stool
3. Change from baseline in plasma biomarkers (eg, cytokines IL-2, IL-6, IL-8, IL-10 and IL-32; heparan sulfate; Reg3 α ; ST2; TNFR1 and IL-1RA) and stool calprotectin concentrations
4. T cell subpopulations from serum, including CD4+ CD25+ CD127+ FoxP3+ Tregs

3.1.3.4 Health Outcomes

1. Change from baseline in QoL as measured by the Functional Assessment of Cancer Therapy-Bone Marrow Transplant subscale version 4.0 instrument (FACT-BMT)
1. Change from baseline in acute GvHD symptoms as measured by the Chronic GvHD Symptom Scale
2. Change from baseline in health utility as measured by European Quality of Life-5 Dimensions-5 Level (EQ-5D-5L)
3. Healthcare resource utilization:
 - type of admission (Hospital, Intensive Care Unit and/or transplant unit)
 - length of stay
 - Number of unscheduled physician office visits
 - Number of emergency room visits
4. Medication:
 - Days on steroids

4. ANALYSIS SETS

4.1 Efficacy Analysis Set

The Efficacy Analysis set will include all subjects who are evaluable for overall response at Day 28. Subjects who do not receive at least 1 dose or who are withdrawn due to a lower GI biopsy that is inconsistent with acute GvHD will not be considered evaluable.

The Efficacy Analysis set will be used for the primary analysis of the primary outcome measure and the analyses of selected secondary efficacy outcome measures and health outcomes.

4.2 Safety Analysis Set

The Safety Analysis (SAF) set will consist of all subjects who receive at least 1 dose of study treatment and will be used in the analyses of safety variables, and the sensitivity analyses of the GvHD overall response rate at Day 28 and GI response rate at Day 28.

4.3 PK Analysis Set

The PK Analysis set will consist of all subjects in the SAF set who have at least 1 PK or stool sample collected.

4.4 Pharmacodynamic Analysis Set

The pharmacodynamic analysis set will consist of all subjects in the SAF set who have at least 1 postdose biomarker sample collected.

5. STATISTICAL CONSIDERATIONS

All derivations, analyses and summaries are not applicable (details in Section 1 and Section 5.3).

For Part 1, all the outcome variables will be summarized descriptively. Based on the characteristics of the study design and lack of a concurrent control arm, formal testing of treatment effects will not be performed.

Statistical summaries described will be provided for all subjects in the analysis set of interest unless otherwise stated.

For efficacy outcome measures, the point estimate and 95% confidence interval will be provided. For the other outcome measures, continuous variables will be summarized by the number of observations, mean, standard deviation, median, minimum, and maximum. Categorical variables will be summarized by frequency counts and percentages for each

category. Unless otherwise stated, percentages will be calculated out of the total in the analysis set. The number of missing values will be presented where necessary.

For continuous data the mean and median will be rounded to 1 additional decimal place compared to the original data. The standard deviation will be rounded to 2 additional decimal places compared to the original data. Minimum and maximum will be displayed with the same accuracy as the original data. For categorical data, percentages will be rounded to 1 decimal place.

For time-to-event outcome measures, Kaplan-Meier estimates will be provided, and the estimates will include 25th percentile, median and 75th percentile, if estimable, and the corresponding 95% confidence intervals.

5.1 Handling of Missing, Unused, and Spurious Data

For Part 1, for the primary analysis of GvHD overall response, the non-responder imputation (NRI) approach will be used to impute the response status at Day 28 as no response for subjects without a response assessment at Day 28 due to any reason. The NRI approach will also be applied to GI response at Day 28 and other time point responses, including overall response at Day 56.

Regarding missing data in AE records:

- Handling of unknown causality assessment:
 - If a subject experiences an AE with a missing causality assessment, the relationship of the AE will be counted as “related”.
- Handling of unknown severity grades:
 - If a subject experiences more than one AE categorized under the same preferred term, the subject will be counted under the most severe toxicity grade reported for that AE.
 - If a subject experiences an AE and the toxicity grade was not provided, the toxicity grade of this AE should be counted as “unknown”. A row or column labelled “Unknown” should be inserted for those AEs in tables where AEs are summarized by toxicity grade.

5.2 Definition of Baseline

Baseline will be the last non-missing assessment of the variable under consideration prior to initial administration of study treatment (GLASSIA in Part 1).

Assessments on the day of first dose of study treatment where time is not captured will be considered as after the first dose unless a nominal pre-dose indicator is available or such procedures are required by the protocol to be conducted before the first dose of study treatment.

5.3 Changes from the Planned Statistical Analysis in Protocol

As indicated in Section 1, Shire (sponsor) prematurely terminated the entire study (both Part 1 and Part 2) on 2 June 2017 following an internal portfolio prioritization exercise which took into consideration difficulties in enrolling subjects and a reduced probability of success of the study. As of the decision date, only 1 subject had been enrolled in the study and no additional subject will be enrolled. That subject was treated with study drug under the original protocol because Protocol Amendment 1, while approved on 19 April 2017, prior to the study termination date, could not be implemented.

This SAP is for Part 1 of the 2-part study and is based on the original protocol and thus documents all derivations of outcome variables, statistical analyses and summaries preplanned in the original protocol. Unless otherwise specified in this SAP, only data listings will be produced for the single-enrolled subject, and the listings will include raw (actual) values. In addition, since no adjudication of the response assessment data will be done, only the data based on the investigators' assessments will be presented in the listings.

6. STUDY SUBJECTS

All derivations, analyses and summaries are not applicable (details in Section 1 and Section 5.3).

6.1 Disposition of Subjects

Subject disposition will be summarized and presented with the number and percentage of subjects who were screened, screen-failed, treated, completed the study, and discontinued early (including reasons for discontinuations). The number and percentage of subjects in each analysis set (SAF, Efficacy, PK) will be displayed. A listing of subject disposition will be produced. Inclusion/exclusion criteria violations will be listed for screen-failed subjects.

6.2 Demographic and Baseline Characteristics

Demographic and baseline characteristics, including age (years), sex, race (where applicable), ethnicity (where applicable), height (cm), weight (kg), BMI (kg/m²),

baseline GvHD stages as measured as the degree of skin, GI, liver involvement, severity grade of acute GvHD, stage of lower GI involvement, status of recurrent malignancy at baseline, and transplant history (source of HSCT, donor related or not, sex of donor, primary or repeated transplant) will be summarized using descriptive statistics. Age will be calculated as the integer of (Date of Informed Consent – Date of Birth)/365.25.

Smoking history will be categorized (never, current, former) for each nicotine type and presented separately. Details of smoking history, including the age of starting and quitting smoking, daily amount, and pack years, will be listed only.

Summaries will be provided for the SAF and Efficacy Analysis sets for all subjects in each analysis set. Demographics and baseline characteristics will also be presented in subject data listings.

6.3 Medical History

The medical and surgical history of subjects will be coded using the Medical Dictionary for Regulatory Activities (MedDRA), version 19.1 or a later version and summarized separately for the SAF set, presenting the number and percentage of subjects with a history in each system organ class (SOC) and preferred term. For summary tables, a subject will be counted only once per body system and preferred term. Medical and surgical history will be included in data listings. Acute GvHD history will be listed only.

6.4 Concomitant Medications

Other than the study drug, any medications or therapies administered on or after the first dose of study treatment but not starting after the last dose of study treatment, or with a start date prior to and an end date on or after the date of the first dose of study treatment, or marked as ongoing will be considered concomitant medications. Medications that ended prior to the date of the first dose of the study drug will be considered as prior medications. Concomitant and prior medications will be coded using the latest version of the WHO Drug dictionary and summarized separately.

Concomitant anti-infective medications will be summarized by re-grouping antibiotics, antivirals, and antifungals agents, with the number and percentage of subjects using each concomitant medication according to the WHODRUG Anatomic Therapeutic Class (ATC) and preferred term for the SAF set. Subjects with multiple uses of a concomitant medication will be counted once by the drug class and preferred term.

Prior and concomitant medications will be presented in the subject data listings.

6.5 Protocol Deviations

Protocol deviations will be classified as Minor, Important/Major or Critical/Priority. For analysis and reporting purposes, deviations leading to exclusion from the Efficacy Analysis set will include, but are not limited to: deviation from eligibility criteria, administration of prohibited medications and erroneous administration of study treatment. The criteria for grading protocol deviations will be proposed according to Quintiles SOP by the Quintiles Therapeutic Medical Advisor and aligned with the Baxalta Physician. All protocol deviations leading to exclusion from the Efficacy Analysis set are determined together with the Baxalta Physician on a case-by-case basis by the medical reviewer prior to each database lock of Part 1.

The number and percentage of subjects for each type of protocol deviation will be tabulated for the SAF set and a listing will be produced showing individual subjects for all protocol deviations.

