10.4 Medications and Non-Drug Therapies

The following medications and non-drug therapies are **not** permitted within 30 days before study entry and during the course of the study:

- Medications:

- Any IP other than GLASSIA (GLASSIA is also not permitted prior to the first administration of study treatment)
- Any GvHD treatment (eg, antithymocyte globulin, anti-TNF drugs) other than 1) prophylactic therapies started prior to study entry and 2) corticosteroid therapy as described below
- Prophylactic GvHD therapies started after study entry
- Enteral corticosteroids
- Non-drug therapies:
 - Any investigational device

A subject who has taken any of these medications or received any of these non-drug therapies will be discontinued from study treatment, and the medication/non-drug therapy will be considered a protocol deviation.

Second-line GvHD treatment may be introduced per investigator discretion prior to Day 28 if a subject experiences disease progression and/or new organ involvement or no change in acute GvHD status after at least 7 days of study treatment (Day 6). Subjects receiving second-line treatment prior to Day 28 must be withdrawn from study treatment; if the subject meets the criteria for introducing second-line treatment prior to Day 28, the second-line treatment will not be considered a protocol deviation. Refer to Section 8.2 for additional details about second-line treatment.

The following medications and non-drug therapies are permitted before study entry and during the course of the study:

- Medications:
 - Corticosteroid therapy for acute GvHD with lower GI involvement (treatment must have been initiated no more than 72 hours prior to the first administration of study treatment)
 - Prophylactic GvHD therapies started prior to study entry (eg, cyclosporine and/or mycophenolate mofetil, etc)
 - Topical corticosteroids including ophthalmic steroids
 - Any medications other than those listed as not permitted above
- Non-drug therapies:
 - Any non-drug therapies other than those listed as not permitted above

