13. STATISTICS

13.1 Sample Size and Power Calculations

Part 1:

The sample size for Part 1 was determined from an operational perspective and was not based on statistical power considerations. With 20 evaluable subjects and an assumed true response rate of 65%, the probability of observing an overall response rate of at least 55% is 87.8%. If the true response rate is 40%, the probability of observing an overall response rate of 55% or higher is less than 13%.

Part 2:

The primary endpoint for Part 2 is the overall response rate at Day 28.

The null hypothesis for Part 2 is that there is no difference in the overall response rate at Day 28 between the 2 treatment groups. The alternative hypothesis is that the overall response rate at Day 28 of the GLASSIA group is higher than that of the control group.

To determine the sample size for Part 2, the following assumptions were used:

1. Control group overall response rate of 40% across strata
2. GLASSIA group overall response rate of 65% across strata
3. Randomization ratio 1:1
4. 1-sided family wise Type I error rate of 0.025
5. Type II error rate of 0.20 (ie, power=80%)
6. A group sequential design with 1 interim look will be applied to the study. The gamma error spending function³¹ with a parameter -2 will be used for beta spending (nonbinding). The interim analysis will take place when approximately 50% of the primary endpoint data has been accumulated

SAS version 9.4, PROC SEQDESIGN with stop=both and nonbinding option for beta, and a gamma parameter of -40 for alpha spending (and hence no alpha spent) and -2 for beta spending was used to calculate this design.

Based on the sample size calculations, using a Cochran-Mantel-Haenszel chi-squared test, controlling the stratification factor, to detect the difference between the 2 groups, the primary analysis will require 67 evaluable subjects per group. Assuming a 10% early withdrawal rate, the target number of subjects will include 74 randomized subjects per group for a total of 148 randomized subjects.

The early withdrawal rate will be monitored in a blinded manner, and if found to be greater or less than 10%, sample size assumptions may be revised.

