13.2 Analysis Sets

Part 1

The **Efficacy Analysis set** will include all subjects who are evaluable for overall response at Day 28. Subjects who receive at least 1 dose of study treatment and who have a lower GI biopsy that is consistent with acute GvHD will be considered evaluable.

The **Per-Protocol Analysis set** will include all subjects who received at least 1 dose of study treatment, meet all key eligibility criteria, and have no major or clinically significant protocol deviations. Major protocol deviations that will lead to exclusion from this set will be determined prior to each database lock.

The **Safety Analysis (SAF) set** will consist of all subjects who receive at least 1 dose of study treatment.

The **PK Analysis set** will consist of all subjects in the SAF set who have at least 1 PK or stool sample collected.

Part 2

The **Full Analysis (FA) set** will include all subjects who are randomized at Day 0. Following the intent-to-treat principle, subjects will be analyzed according to the treatment they are assigned to at randomization.

The **Per-Protocol Analysis set** will include all subjects who received at least 1 dose of study treatment, meet all key eligibility criteria, and have no major or clinically significant protocol deviations with a lower GI biopsy consistent with acute GvHD and without a major protocol deviation. Major protocol deviations that will lead to exclusion from this set will be prespecified prior to unblinding the treatment codes.

The **SAF set** will consist of all subjects who receive at least 1 dose of study treatment. Subjects will be analyzed according to the treatment received.

The **PK Analysis set** will consist of all subjects in the SAF set who have at least 1 PK or stool sample collected.

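### SAP 6.5 lets protocol deviations, including prohibited medication, remove dosed subjects from the Part 1 primary efficacy set, against SAP 4.1, the treatment-failure rule and protocol 13.2

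*SAP*

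**What the plan says.** **Definition of the set.** SAP 4.1 bases the Efficacy Analysis set on evaluability for Day 28 response. Subjects without a dose, or "who are withdrawn due to a lower GI biopsy that is inconsistent with acute GvHD will not be considered evaluable", are left out. No other exclusion appears there, and the section makes this the set for the primary analysis.

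**Deviation rule.** SAP 6.5 names deviations that lead to exclusion from the same set: "deviation from eligibility criteria, administration of prohibited medications and erroneous administration of study treatment". The list is expressly not exhaustive. Exclusions are settled individually by the medical reviewer with the sponsor's physician before each Part 1 database lock.

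**Treatment failures.** SAP 2 states: "Subjects classified as treatment failures will be included in the analysis but not be counted as either complete response (CR) or partial response (PR"). Protocol 8.2 has the same rule.

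**Prohibited medication.** Protocol 10.4 bars "Any GvHD treatment (eg, antithymocyte globulin, anti-TNF drugs) other than" prophylaxis begun before entry and the permitted corticosteroids. It then says that second-line treatment before Day 28 is not a deviation if the criteria for introducing it are met. SAP 6.5 does not repeat that exemption.

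**Current protocol.** Protocol 13.2 (Amendment 1) counts as evaluable "Subjects who receive at least 1 dose of study treatment and who have a lower GI biopsy that is consistent with acute GvHD". It places the exclusion for major deviations in a separate Part 1 Per-Protocol set, which the SAP does not define.

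**The concern.** The SAP gives two incompatible definitions of the set that carries its primary analysis. Under SAP 4.1 and SAP 2, a dosed subject whose disease is treated with another GvHD drug stays in and counts as a non-responder. Under SAP 6.5, the same subject may be removed if the drug was given outside the second-line criteria, because it is then a prohibited medication and a deviation.

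That kind of exclusion is likely to be related to outcome, since extra GvHD treatment tends to be given to subjects who are doing badly. It is also decided when the outcome can be seen: Part 1 is open-label (SAP 2.3), the primary analysis uses the investigators' assessments (SAP 7.1), and exclusions need only be fixed before lock. Non-responder imputation (SAP 5.1) gives no protection, because in the primary analysis it applies only to subjects still in the Efficacy set. The adjudicated sensitivity analysis uses the same set.

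At stake is the Part 1 response rate, which protocol 8.2.2 compares with 55% when the start of Part 2 is considered.

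**Working it through.** **Inputs**
- Sample size and target rate, from protocol 13.1: "With 20 evaluable subjects and an assumed true response rate of 65"%.
- Chance of passing on that basis, from the same sentence in 13.1: "the probability of observing an overall response rate of at least 55% is 87.8"%.
- Chance of passing at the lower rate, also from 13.1: "If the true response rate is 40%, the probability of observing an overall response rate of 55% or higher is less than 13"%.
- Protocol 8.2.2: criterion of at least 55% at Day 28.
- Assumption: k, the number of dosed subjects excluded. The documents give no exclusion rate, so a range is shown.
- No replacement of excluded subjects. Protocol 8.2.1 replaces only those whose biopsy proves inconsistent.

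**Step 1. Reproduce the plan's figures.** 0.55 × 20 = 11 responders. With X ~ Binomial(20, p):
- P(X ≥ 11 | p = 0.65) = 0.8782, stated as 87.8%.
- P(X ≥ 11 | p = 0.40) = 0.1275, stated as less than 13%.

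Both agree.

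**Step 2. All k excluded subjects are non-responders.** The cut-off becomes r = 0.55 × (20 − k), rounded up, but the responders still come from all 20 dosed subjects, so the chance of meeting the criterion is P(X ≥ r) with X ~ Binomial(20, p).

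**Step 3. Exclusions unrelated to response.** The same cut-off r applies, but X ~ Binomial(20 − k, 0.40).

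| k | Left in set | 0.55 × (20 − k) | r | Step 2, p = 0.40 | Step 2, p = 0.65 | Step 3, p = 0.40 |
|---|---|---|---|---|---|---|
| 0 | 20 | 11.00 | 11 | 0.1275 | 0.8782 | 0.1275 |
| 1 | 19 | 10.45 | 11 | 0.1275 | 0.8782 | 0.0885 |
| 2 | 18 | 9.90 | 10 | 0.2447 | 0.9468 | 0.1347 |
| 3 | 17 | 9.35 | 10 | 0.2447 | 0.9468 | 0.0919 |
| 4 | 16 | 8.80 | 9 | 0.4044 | 0.9804 | 0.1423 |
| 5 | 15 | 8.25 | 9 | 0.4044 | 0.9804 | 0.0950 |

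For example, 10 of 20 (50%) misses the criterion, but after two non-responders are removed it becomes 10/18 = 55.6% and meets it. With four removed, 9 of 20 (45%) becomes 9/16 = 56.3%.

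**Step 4. Whom the prohibited-medication route reaches.**
- Second-line treatment that meets the protocol 10.4 criteria: not a deviation, so not reached.
- Methylprednisolone or equivalent above 2 mg/kg/day for GvHD: a treatment failure under protocol 8.2, but not a listed prohibited medication, so not reached.
- Another GvHD drug given outside the criteria: prohibited and a deviation, so reached. How many subjects this covers depends partly on whether the 7-day condition in 10.4 applies to progression as well as to unchanged disease; the sentence can be read either way.
- A treatment failure who also has an eligibility or dosing deviation: reached through the other items in SAP 6.5.

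**The case against.** The strongest reply is that the consequence is small and partly guarded against.

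- **The criterion is nonbinding.** Protocol 8.2.2 says the study may proceed or may be stopped, on the totality of the data, with the sponsor deciding. No passage names the denominator for the 55%. This stands: a reader might infer that SAP 6.5 by itself decides whether Part 2 starts, and the documents do not support that. The Efficacy set is the natural reading only because it is the primary set and the stated probabilities rest on evaluable subjects.
- **The route is narrow.** This also stands, as Step 4 shows. A reader might infer that treatment failures in general drop out; most would not by this route.
- **The larger percentages are a worst case.** They require every excluded subject to be a non-responder. Eligibility and dosing deviations can remove responders too, and Step 3 shows that unrelated exclusions do little.
- **A sensitivity analysis on all dosed subjects would expose the loss.** Protocol 13.4.1 and SAP 4.2 mention one on the Safety Analysis set. However, the SAP 7.1 table, presented as listing all planned analyses of this endpoint, omits it, so this safeguard is only partly in place.
- **Biopsy.** A reader might infer a second route: protocol 13.2 requires a consistent biopsy, so a dosed subject who dies or deteriorates before biopsy is lost, whereas SAP 4.1 keeps that subject. The wording does differ, but the window is short, a missing biopsy is not the same as treatment failure, and the SAP follows the original protocol while 13.2 is Amendment 1. It is a point to align, not a demonstrated bias.

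The version difference does not explain the conflict of SAP 6.5 with SAP 4.1 and SAP 2, which lies inside one document.

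**Conclusion.** The contradiction is real. Followed as written, SAP 6.5 permits outcome-related exclusions from the primary Part 1 set that SAP 4.1, SAP 2 and protocol 8.2 do not allow and that protocol 13.2 reserves for the Per-Protocol set.

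The size depends on an assumed number of exclusions, all non-responders and none replaced: at a true rate of 40%, no change for one, roughly a doubling for two or three, and roughly a tripling for four or five (Step 2). If exclusions are unrelated to response there is no material inflation.

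A reader might conclude that the plan's 87.8% and less than 13% are wrong. They are not: both hold for 20 evaluable subjects with no outcome-related exclusions.

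This is a flaw in the plan, not in a result. The study was terminated with one subject enrolled, and the SAP marks these analyses as not applicable and provides only listings for the response data.

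**What to change.** 1. In SAP 6.5, delete the deviation-based exclusions from the Efficacy Analysis set. Apply them only to a Per-Protocol set, which SAP section 4 must add from protocol 13.2.
2. Add the Safety Analysis set sensitivity analysis to the SAP 7.1 table, so that it agrees with SAP 4.2 and protocol 13.4.1.
3. In protocol 8.2.2 and 13.5, name the Efficacy Analysis set as the denominator for the 55% criterion.
4. Align protocol 13.2 with SAP 4.1, so that a dosed subject with no biopsy result stays in as evaluable and only a biopsy shown to be inconsistent removes a subject.

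The cost is wording in a few sections plus one added analysis set. Keeping such subjects in makes the expected Part 1 response rate slightly lower. With the study closed, the change matters for the documented plan and for any reuse of it.
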